**APPENDIX D: MEDICAL ADJUDICATION RULES ASTX727-02 STUDY**

This is a working document and may require updating from time to time.

**1. 100 nucleated cells requirement**

- a. EDC was not designed correctly to capture whether >100 nucleated cells were evaluated on aspirate
  - i. Solution - in EDC, it was asked was the aspirate "sample adequate"?
    1. If yes, use data as quantified by hematopathologist
    2. If answer is blank or "sample not adequate" then options are:
      - a. Try to obtain redacted hematopathology report, or
      - b. If not possible, send investigator a form that requires them to indicate that the BM evaluation was overall adequate for response assessment (e.g., tissue biopsy was used to evaluate blast count and response assessment). File an administrative letter or as appropriate.

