### 7.5.1 Response Rate

The evaluation of response (Table 2) will be based on Modified IWG 2003 AML Response Criteria (Cheson et al 2003), and include CRp according to the DACO-016 study (Kantarjian et al 2012) for that CRp is not any response category of IWG 2003 AML Response Criteria (Cheson et al 2003). Subjects who do not have a valid post-treatment efficacy assessment (ie, no post-treatment BM/PB sample or the quality of BM/PB sample is not adequate for an assessment of efficacy) will be classified as not evaluable (NE) for response classifications. Subjects who cannot be classified into a response category (CR, CRi, or PR) or into the NE category will be classified as non-responders (NR). According to the recommendations of the European LeukemiaNet (Döhner et al 2017), progressive disease is defined as >50% increase in marrow blast % from baseline (15% increase in cases with <30% marrow blasts at baseline); or >70% marrow blasts over at least 3 months; or >50% increase in peripheral blasts to  $\geq 25 \times 10^9/L$  ( $\geq 25,000/\mu L$ ); and stable disease is defined as absence of CR, CR subtype, PR and progressive disease for at least 3 months. CRh, CR with partial hematologic recovery, is defined as <5% of blasts in the bone marrow, no evidence of disease, and partial recovery of peripheral blood counts (platelets  $>50,000/\mu L$  and ANC  $>500/\mu L$ ) (Kantarjian et al 2017). Evaluation of response will be conducted by Astex medical monitors assisted by programmed data listings, as detailed in the Astex AML Response Assessment Criteria (Section 8.1).

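### SAP Appendix D, rule 1: the fallback form for doubtful marrows is worded for one answer and states no return to not evaluable, so any error can only raise AML response rates or leave them unchanged

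*SAP*

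**What the plan says.** SAP Section 7.5.1 defines who is not evaluable: a subject with no valid efficacy assessment after treatment is counted as NE. It explains the absence of a valid assessment as "no post-treatment BM/PB sample or the quality of BM/PB sample is not adequate for an assessment of efficacy". The same section says that "Evaluation of response will be conducted by Astex medical monitors assisted by programmed data listings", and refers to Section 8.1 for the detail.

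Section 8.1 contains Appendix D, whose first rule deals with the minimum of 100 nucleated cells. It starts from an acknowledged data gap: "EDC was not designed correctly to capture whether >100 nucleated cells were evaluated on aspirate". The database asked instead whether the aspirate sample was adequate. The rule then has these branches:

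- If the answer is yes, the hematopathologist's figures are used.
- If the answer is blank or not adequate, the first option is to obtain a redacted hematopathology report.
- If that is not possible, the instruction is to "send investigator a form that requires them to indicate that the BM evaluation was overall adequate for response assessment". Use of the tissue biopsy to count blasts is offered as an example, and the matter is to be filed by administrative letter or as appropriate.

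Three other parts of the SAP bear on the effect. The Efficacy Analysis Set (Section 5.3) is all subjects who received any study treatment. Section 7.5.1 summarizes each subject by best response across visits. The table shell in Appendix E shows NE as a row among the response categories.

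**The concern.** The form is described as having one possible outcome. It is reached from a blank answer and also from an explicit record that the aspirate was not adequate. The rule names no answer for an inadequate marrow, requires no documented basis, and does not say when the marrow stays invalid so that the subject is NE.

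The form is completed after the fact in an open-label study, by an investigator who may know the blast count and the clinical course. If it leads to a marrow being accepted wrongly, the error favors response. CR, CRi, CRp, CRh and PR all depend on the marrow blast count, and Appendix C sends the 100-cell requirement for each of them to Appendix D. At stake are the AML response rates and how they are described. The shell's footnote says that subjects with inadequate sample quality were classified as NE, and a reader of the table could not see how many marrows had been accepted on the form alone.

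**Working it through.** The documents give no response rate, NE count or count of form-only marrows, so there is no figure to reproduce. The check has two parts.

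**Comparing the provisions**

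- *What is judged.* Section 7.5.1 asks whether a subject has any valid post-treatment marrow or blood assessment. The database item in rule 1 concerns the aspirate of one marrow. A poor aspirate with a readable biopsy is not NE under 7.5.1, and neither is a subject with one poor marrow among several.
- *Where they collide.* Take a subject whose only post-treatment marrows have an inadequate aspirate, no obtainable report and no usable biopsy. Section 7.5.1 gives NE. Rule 1 sends a form that asks for a statement of adequacy and does not say what follows if adequacy cannot be supported.

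**Direction and size**

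Let N be the number of treated subjects, x the responders without form-only marrows, and k the subjects moved from NE to responder by a form alone. NE subjects remain in N, so

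change = (x + k)/N − x/N = k/N, which is never negative.

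Best response is used, so one more accepted marrow can improve a subject's category but cannot worsen it. A subject moved from NE to stable disease, progressive disease or non-responder contributes k = 0.

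Inputs:

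- N = 85 is assumed from the planned number randomized in SAP Section 4.0; the treated number is not given. N = 70, the planned evaluable number, is the alternative.
- k and x are not in the documents. The values below are illustrations only.

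Per subject: 1/85 = 1.2 points, or 1/70 = 1.4 points.

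With an assumed x = 17 of 85 and the SAP's Clopper-Pearson interval:

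| k | Rate | 95% CI |
|---|---|---|
| 0 | 17/85 = 20.0% | 12.1 to 30.1 |
| 1 | 18/85 = 21.2% | 13.1 to 31.4 |
| 2 | 19/85 = 22.4% | 14.0 to 32.7 |
| 4 | 21/85 = 24.7% | 16.0 to 35.3 |
| 8 | 25/85 = 29.4% | 20.0 to 40.3 |

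The shift for a given k does not depend on x: 1 to 8 subjects add 1.2 to 9.4 points at N = 85.

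**The case against.** The strongest reply is that rule 1 carries out Section 7.5.1 and does not compete with it. Section 7.5.1 itself points to Section 8.1. The pathology report comes first and can confirm that a marrow was inadequate; the form is only a fallback. The criteria table in Section 8.1 asks for a rule where the cell count is missing or near 100, or where only a biopsy exists. The supplied protocol (schedule of events, bone marrow note) also accepts a biopsy when there is no aspirate. Where a biopsy truly supports the blast count, leaving the subject NE would understate response. The investigator is asked about adequacy only, and sponsor medical monitors assign the response. The form is not among the documents, so its answer options may be wider than the rule's wording suggests.

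Most of this stands, and it narrows the point. It does not remove it. The biopsy is an example in rule 1, not a requirement, and nothing in the rule says when a marrow remains invalid.

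A reader might infer that the SAP flatly contradicts itself. It does so only where no other adequate material exists. A reader might also infer that adjudication under this rule can only favor the drug. That is not so: Appendix C applies the same 100-cell item to stable disease, progressive disease and relapse, and an accepted marrow showing progression or relapse can shorten duration of response, EFS or PFS (Sections 7.5.3, 7.5.7 and 7.5.8). Only the response-rate numerator moves one way.

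**Conclusion.** The point holds as a one-directional risk in a stated rule. A marrow with a blank or negative aspirate record and no obtainable report can be accepted on a form worded for one answer, with no required basis and no stated route back to NE. For a subject with no other adequate material, this can override Section 7.5.1.

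The size is about 1.2 points per subject moved from NE to responder, assuming 85 treated subjects. The total is unknown and may be zero, because the number of such marrows is not given and accepted marrows may show no response. A reader might conclude that the reported response rates are biased upward. The documents do not support that; they show only that an error here could not lower them.

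The affected endpoints are secondary and descriptive, with no formal comparison between sequences (Section 7.5), and the primary pharmacokinetic endpoint is unaffected. The change is a cheap improvement.

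**What to change.** - Make the form neutral: adequate, not adequate, or cannot say, with the documented basis, such as a biopsy blast count or the number of cells counted. Have it completed without reference to the response call.
- Add one sentence to Appendix D, rule 1: a marrow without a documented basis for adequacy is not a valid assessment, and the subject is NE under Section 7.5.1 if no other valid assessment exists.
- Report the number of marrows accepted on the form alone.
- Add one sensitivity row to the response table that treats those marrows as not adequate.

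The cost is form wording, one SAP sentence, one count and one table row. The downside is possibly a few more NE subjects and slightly lower response rates. Appendix D describes itself as a working document open to updating, so the change fits its own terms.

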**2. Peripheral blasts**

- a. If  $\leq 1\%$  and other CR/CR subtype criteria met, can assume part of regenerating marrow process
- b. If  $>1\%$  and other CR/CR subtype criteria met, use at least one follow-up CBC with differentials to confirm CR/CR subtype criteria (blasts should lessen over days and become  $\leq 1\%$ )
3. Transfusions within 1 week of a CR or CR subtype (expecting to be a rare occurrence)
  - a. If CR/CR subtype criteria met and there is a documented RBC or platelet transfusion within 1 week, consider clinical circumstances of the transfusion - reviewing EDC (AEs, medical hx, concomitant procedures) or asking investigator for details (document and file an administrative letter or as appropriate). This will cover the rare circumstance when the subjects are transfused electively for a medical history, AE, or procedure.

**4. BM/CBC not on same day (priority of evaluation order)**

- a. Evaluate response using BM biopsy and CBC with differential from the same day
- b. If not matched, look for the closest CBC (usually should be  $\pm 1$  week); assess response using the combination of data and use the later of the two dates as first response
- c. If a marrow is done and a CBC  $>1$  week later shows additional count recovery and meets a new response, enter response at date when CBC data shows criteria met (ask sites to enter any interim missing weekly labs)
- d. If two CBCs are done with the same # days from the marrow and show the same response, use the marrow date for response assessment; if one CBC shows a better response use that CBC and use the date of that CBC
- e. If two CBCs are done with the same # days ( $\pm$ ) from the marrow and show the same response, use the marrow date for response assessment; if the later CBC shows a better response use that CBC date; if the earlier CBC shows a better response, use the BM biopsy date
- f. Note: since CBC with differential on a weekly basis may be critical for proper dating of changes in response assessment (e.g., subject with SD and progressing towards a CR), ask sites to add weekly labs even if local labs (pass to DM to query for all missing weekly labs)

**5. No interim BM and CR is achieved on a later CBC**

- a. If MLFS (morphologic leukemia-free state), can assess a CR or CR subtype based on a later CBC with diff showing count recovery to meet criteria
- b. If CR subtype (includes MLFS), can assess a CR based on a later CBC with diff showing count recovery to meet criteria
- c. If PR (blasts 5-20%) or SD, cannot assess a higher response category based on a later CBC with diff without a BM evaluation

6. Bone Marrow Blasts Percentages

- a. If BM  $\geq 5\%$  is not seen on laboratory values at screening, to be evaluable, there must be evidence in the EDC supporting the AML diagnosis (BM  $\geq 5\%$ ). To rule out the possibility this is a protocol violation (patient does not have a diagnosis of AML), documentation of either 1) any pre-screening maneuvers that reduced blasts (eg hydroxyurea or single dose of cytarabine or mitoxantrone) or 2) the subject has peripheral blasts  $>20\%$  but not marrow blasts  $>20\%$ , or 3) the subject presents as a myeloid sarcoma which is a type of AML that grows as a tumor and may have a marrow that does not reach AML blast count or is even completely normal. If there is a bone marrow before the screening marrow that documents the AML before #1, ask the site to add the data as an unscheduled BM and date it accordingly for proper documentation and verification of the AML diagnosis. These are the typical circumstances when subjects with AML have blasts  $<20\%$  at baseline.
- b. BM blasts fall from above to below 5% then return above and below 5% again. This may be due to BM rejuvenation. Requires medical adjudication to determine if still in best response or relapsing. Answer to this should be apparent over time.

**APPENDIX E: STANDARD BDM TABLE OUTPUTS OF RESPONSE ASSESSMENT**(1) using 2003 IWG and [Kantarjian et al 2017](#)

Taking ASTX727-02 AML as a sample:

**ASTX727-02 EMEA AML Submission****Population: Efficacy Analysis Set**

**Table xx.x.x**  
**Analysis of Overall Response**

	Sequence A (N=xx)		Sequence B (N=xx)		Total (N=xx)	
	n (%)	95% CI	n (%)	95% CI	n (%)	95% CI
Best Response						
CR	xx (xx.x)	(xx.x, xx.x)	xx (xx.x)	(xx.x, xx.x)	xx (xx.x)	(xx.x, xx.x)
CRi	xx (xx.x)	(xx.x, xx.x)	xx (xx.x)	(xx.x, xx.x)	xx (xx.x)	(xx.x, xx.x)
CRp	xx (xx.x)	(xx.x, xx.x)	xx (xx.x)	(xx.x, xx.x)	xx (xx.x)	(xx.x, xx.x)
PR	xx (xx.x)	(xx.x, xx.x)	xx (xx.x)	(xx.x, xx.x)	xx (xx.x)	(xx.x, xx.x)
SD	xx (xx.x)	(xx.x, xx.x)	xx (xx.x)	(xx.x, xx.x)	xx (xx.x)	(xx.x, xx.x)
PD	xx (xx.x)	(xx.x, xx.x)	xx (xx.x)	(xx.x, xx.x)	xx (xx.x)	(xx.x, xx.x)
NE	xx (xx.x)	(xx.x, xx.x)	xx (xx.x)	(xx.x, xx.x)	xx (xx.x)	(xx.x, xx.x)
Composite Response Rates						
CR + CRi	xx (xx.x)	(xx.x, xx.x)	xx (xx.x)	(xx.x, xx.x)	xx (xx.x)	(xx.x, xx.x)
CR + CRi + PR	xx (xx.x)	(xx.x, xx.x)	xx (xx.x)	(xx.x, xx.x)	xx (xx.x)	(xx.x, xx.x)
CR + CRp	xx (xx.x)	(xx.x, xx.x)	xx (xx.x)	(xx.x, xx.x)	xx (xx.x)	(xx.x, xx.x)
CR + CRh	xx (xx.x)	(xx.x, xx.x)	xx (xx.x)	(xx.x, xx.x)	xx (xx.x)	(xx.x, xx.x)
CRh 	xx (xx.x)	(xx.x, xx.x)	xx (xx.x)	(xx.x, xx.x)	xx (xx.x)	(xx.x, xx.x)

The 95% CI is Clopper-Pearson confidence interval.

CR=complete response; CRp=complete response with incomplete platelet recovery; CRi=CR with incomplete blood count recovery; PR=partial response; SD = Stable Disease; PD = Progressive Disease;

NE=Not evaluable. Subjects who did not have a valid post-treatment efficacy assessment (ie, no post-treatment BM/PB sample or the quality of BM/PB sample is not adequate for an assessment of efficacy) were classified as NE for response classifications.

(1) Modified 2003 IWG response criteria ([Cheson et al. 2003](#)) and DACO-016 CSR was used for CR, CRi, CRp, PR, SD, and PD, and NE.(2) [Kantarjian et al 2017](#) was used for the CRh assessment.

Sequence A: ASTX727 in Cycle 1; IV decitabine in Cycle 2. Sequence B: IV decitabine in Cycle 1; ASTX727 in Cycle 2.

Program Location: *m:\astx727\02\biostat\phase3\_eu\devel\program\tables\t\_response1.sas*, Data Cut Off: 04JUN2021, Database Extracted: 16JUL2021  
 Output: *t\_14.3.1\_response1.rtf* (Date Generated: 01SEP2021:13:56), Source Data: ADAMDATA.ADSL, ADRS

(2) ) using [2017 ELN](#) and [Kantarjian et al 2017](#)

<Protocol>

Population: <Analysis Set>

**Table xx.x.x**  
**Analysis of Overall Response**

	Group 1 (N=xx)		... (N=xx)		Total (N=xx)	
	n (%)	95% CI	n (%)	95% CI	n (%)	95% CI
Best Response						
CR	xx (xx.x)	(xx.x, xx.x)	xx (xx.x)	(xx.x, xx.x)	xx (xx.x)	(xx.x, xx.x)
CRi	xx (xx.x)	(xx.x, xx.x)	xx (xx.x)	(xx.x, xx.x)	xx (xx.x)	(xx.x, xx.x)
PR	xx (xx.x)	(xx.x, xx.x)	xx (xx.x)	(xx.x, xx.x)	xx (xx.x)	(xx.x, xx.x)
SD	xx (xx.x)	(xx.x, xx.x)	xx (xx.x)	(xx.x, xx.x)	xx (xx.x)	(xx.x, xx.x)
PD	xx (xx.x)	(xx.x, xx.x)	xx (xx.x)	(xx.x, xx.x)	xx (xx.x)	(xx.x, xx.x)
NE	xx (xx.x)	(xx.x, xx.x)	xx (xx.x)	(xx.x, xx.x)	xx (xx.x)	(xx.x, xx.x)
Composite Response Rates						
CR + CRi	xx (xx.x)	(xx.x, xx.x)	xx (xx.x)	(xx.x, xx.x)	xx (xx.x)	(xx.x, xx.x)
CR + CRi + PR	xx (xx.x)	(xx.x, xx.x)	xx (xx.x)	(xx.x, xx.x)	xx (xx.x)	(xx.x, xx.x)
CR + CRh	xx (xx.x)	(xx.x, xx.x)	xx (xx.x)	(xx.x, xx.x)	xx (xx.x)	(xx.x, xx.x)
CRh 	xx (xx.x)	(xx.x, xx.x)	xx (xx.x)	(xx.x, xx.x)	xx (xx.x)	(xx.x, xx.x)

CR=complete response; CRi=CR with incomplete blood count recovery; PR=partial response; SD = Stable Disease; PD = Progressive Disease;

NE=Not evaluable. Subjects who did not have a valid post-treatment efficacy assessment (ie, no post-treatment BM/PB sample or the quality of BM/PB sample is not adequate for an assessment of efficacy) were classified as NE for response classifications.

(1) [ELN 2017](#) AML Response Criteria.

(2) [Kantarjian et al 2017](#) was used for the CRh assessment.

Group 1: ...

Program Location: *m:\...\devel\program\tables\t\_xxx.sas*, Data Cut Off: DDMMYYYY, Database Extracted: DDMMYYYY

Output: *t\_xx.x.x\_xxxx.rtf* (Date Generated: DDMMYYYY:HH:MM), Source Data: ADAMDATA.ADSL, ADRS

---

## 8.2 Appendix 2: Summary of Changes

### Rationale for Version 2.0

Version 2.0 is an update to the AML Response Assessment Criteria.

### Summary of Changes:

- 1) Section [3.2.2](#) The reference for CRp ([Kantarjian et al 2012](#)) is added; “ complete response with partial hematologic recovery (CRh) will also be assessed as a subset of CRi or CRp” is removed.
- 2) [Table 2](#): The criteria for CRi are changed to be consistent with IWG 2003 AML Response Criteria ([Cheson et al 2003](#)) instead of the protocol.
- 3) Section [7.5.1](#): Progressive disease and stable disease are added based on the European LeukemiaNet ([Döhner et al 2017](#)).
- 4) Section [7.5.2](#): Changing CRp, CRi to CRi (or CRp) due to that CRp is the subset of CRi
- 5) Section [7.5.3](#): Duration of CR or CRp is added based on DACO-016 ([Kantarjian et al 2012](#)).

